9.3.2. Spontaneous Bacterial Peritonitis

Spontaneous bacterial peritonitis (SBP) is considered an adverse event of special interest. Suspected or confirmed cases of SBP should be diagnosed and treated per local standard of care. Samples of all available body fluids should be obtained for PCR assessment prior to initiating broad spectrum antibiotic treatment. Subjects who develop SBP should discontinue IP dosing and the event should be reported to the Sponsor within 24 hours.

9.3.3. Pregnancy

If a subject becomes pregnant while participating in this study, information on the pregnancy and outcome will be requested. If a partner of a participating subject becomes pregnant while their partner is participating in the study or 90 days following their participation, information will be requested on the pregnancy and outcome.

9.3.4. Hepato-Renal Syndrome

Hepato-renal syndrome (HRS) is considered an adverse event of special interest. Suspected or confirmed cases of HRS should be diagnosed and treated per local standard of care. Subjects who develop HRS should discontinue IP dosing and the event should be reported to the Sponsor within 24 hours.

9.4. Reporting of Adverse Events

All AEs, serious and nonserious, will be fully documented on the appropriate eCRF. For each AE, the Investigator must provide its duration (start and end dates or ongoing), intensity, assessment of causality, and whether specific action or therapy was required.

All AEs occurring from the time a subject signs informed consent through the safety follow-up period must be recorded on the eCRF. Subjects will be provided with diary cards for recording AEs during follow-up period after discharge from the inpatient unit.

All SAEs, regardless of relationship to SYNB1020/placebo, must be reported to the Sponsor within 24 hours of the Investigator's knowledge. This should be done by faxing the completed SAE Report Form to the Sponsor at the number provided on the SAE Report Form. After the final follow-up visit, only SYNB1020/placebo-related AEs/SAEs need to be collected and reported to the Sponsor, if clinically indicated.

Investigators must follow subjects with AEs/SAEs until event resolution or stabilization, withdrawal of consent, subject loss to follow-up, or death, whichever occurs first.

9.5. Pregnancy

Only females of non-childbearing potential are eligible for study participation.

9.6. Clinical Laboratory Abnormalities

It is the responsibility of the Investigator to assess the clinical significance of all abnormal laboratory values as defined by the appropriate reference range(s). All abnormal values assessed to be of clinical concern and at least possibly related to SYNB1020/placebo or of uncertain causality should be repeated. Persistent abnormal values and changes of possible clinical concern

that remain within the normal range should be followed at the discretion of the Investigator. Of note, due to the underlying condition under study, ammonia values will often fall outside of the reference ranges; clinical significance and follow-up of these abnormal values will be determined by the treating Investigator on an individual subject basis.

An abnormal laboratory value that is not already associated with an AE is to be recorded as an AE if an action on IP dosing is made as a result of the abnormality, if intervention for management of the abnormality is required, or at the discretion of the Investigator.

9.7. Review of Safety Data

The designated pharmacovigilance physician in collaboration with the Medical Monitor will be responsible for the ongoing review and evaluation of safety data, including AEs, clinical laboratory data, and any other safety evaluations, for the duration of the study in accordance with the medical monitoring plan. A Safety Review Committee comprising the Lead Investigator, Medical Monitor, pharmacovigilance physician, and an external disease expert, as needed, will meet at predetermined intervals during the study as well as in response to certain clinical outcomes. At each meeting, the Safety Review Committee will review blinded data from the ongoing study and determine whether the study should continue as planned, be modified, or be terminated. ([Section 4.4](#)). For details refer to the separate Safety Review Committee charter.

10. STATISTICAL METHODS AND DETERMINATION OF SAMPLE SIZE

All evaluations and tabulations will be carried out as described in detail in a statistical analysis plan (SAP), which will be finalized and approved prior to database lock and unblinding.

In addition to the analyses described within this section, interim analyses may be conducted.

10.1. Populations for Analysis

The following populations will be defined:

Safety Population (SAF): All subjects in Part 1 who received at least one dose of SYNB1020 and have at least one post-baseline safety assessment. All randomized subjects in Part 2 who received at least one dose of SYNB1020 or placebo and have at least one post-baseline safety assessment. Subjects will be included in the analysis according to the dose and IP received.

Microbiotic-kinetic (MK) Population: Subjects in the SAF who completed the clinical study and were considered evaluable for analysis of the MK data. Subjects will be included in the analysis according to the dose and IP received.

Pharmacodynamic (PD) Population: Subjects in the SAF who completed the clinical study and were considered evaluable for analysis of the PD data. Subjects will be included in the analysis according to the study part and IP received.

Data will be excluded from the MK and/or PD population in case of any major protocol deviation that may influence the MK and/or PD outcome.

If not indicated otherwise, the analyses of safety endpoints will be conducted based on the SAF and all MK/PD analyses will be performed based on the MK/PD population.

10.2. Safety Variables

Adverse events will be coded using the Medical Dictionary for Regulatory Activities (MedDRA[®]), and the severity of AEs and laboratory abnormalities will be graded using the NCI CTCAE, version 4.03. AEs will be tabulated by SOC and preferred term. Incidence tables of subjects with AEs will be presented for all AEs by maximum severity, SAEs, AEs assessed as related to SYNB1020/placebo, and AEs resulting in discontinuation of study dosing.

Clinical laboratory data, ECGs, and other safety assessments will be presented in by-subject listings and will be presented in tabular format, including absolute values and changes from baseline (if applicable), by study day.

10.3. Microbiotic-Kinetic Variables

The following variables will be calculated from the serial fecal sampling from each subject, if data support calculation. Further details on these calculations will be included in the SAP.

- T_{lag} – the time of the first detectable fecal SYNB1020
- T_{ss} – the time to steady-state
- q_{max} – the maximum observed fecal SYNB1020 qPCR signal
- T_{last} – the time of the last detectable fecal SYNB1020
- Half-life – the time for the fecal SYNB1020 qPCR signal to decline by 50%

A sample will be considered negative for the purposes of SYNB1020 clearance if it is below the limit of quantification or estimated to be below 0.1% of the administered dose.

The microbiotic-kinetic parameters of SYNB1020 will be summarized descriptively.

10.4. Pharmacodynamic Variables

Pharmacodynamic data will be presented in by-subject listings and will be presented in tabular and/or graphical format, including absolute values and changes from baseline, by study day.

10.5. Determination of Sample Size

Part 1: The sample size for the sentinel cohort (6 subjects) is primarily designed for empirical evaluation of safety and tolerability in subjects with cirrhosis.

Part 2: A sample of 24 subjects must complete all 3 ammonia AUC intervals (baseline, Day 5, and Day 6) to detect a 20% reduction in average daily ammonia ($AUC_{0-24}/24$, from a baseline of 70 $\mu\text{mol/L}$) with an approximate significance level of 10% and an approximate power of 90%. Significance and power are approximate based on the assumptions below. The number of subjects assumes that the standard deviation (SD) of spot ammonia is 36.4 $\mu\text{mol/L}$, half of the variance is between subject, and that the SD for average daily ammonia is as little as half that of spot ammonia. The spot ammonia SD is based on a weighted average of SD observed in a prior study of ammonia lowering in a similar population.²³ The variability of AUC may be 50% lower than spot ammonia based on the FDA summary basis of approval for glycerol phenylbutyrate for urea cycle disorders.²⁴

Due to uncertainty in the assumptions of decrease in variability in AUC of ammonia relative to spot measurements in this population, up to 2 interim analyses for sample size re-estimation may occur after at least 12 subjects have completed all ammonia AUC assessments, and the total number of subjects in Part 2 of the study may be increased up to 40 at either point based on the SD of data observed. Additional subjects may be enrolled to ensure that at least the planned number of evaluable subjects complete the study.

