4.5.2. Screening Period

The screening period for all subjects will be up to 45 days prior to admission to the inpatient facility (i.e., Days -51 to -6).

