5. PATIENT POPULATION

5.1. Number of Subjects

Part 1: 6 evaluable subjects are anticipated for enrollment.

Part 2: Approximately 24 to 40 evaluable subjects, defined as subjects who complete all 3 ammonia 24-hour AUC intervals, are anticipated for enrollment.

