10.6. Randomization and Blinding

Part 1: Open-label, all subjects will receive SYNB1020. Neither subjects nor investigators are blinded.

Part 2: Subjects will be randomized in a 1:1 ratio to receive either SYNB1020 or placebo. Randomization will be performed using a computer-generated central randomization scheme maintained by the Sponsor or designee. Both subjects and investigators will be blinded to study compound assignment, as will all other study personnel, with the exception of one unblinded pharmacist at the study site(s). In addition, an unblinded observer will be assigned to this study and will be independent of the study team. The unblinded observer will be able to review unblinded data as needed to aid in study progress, and this individual will be responsible for re-evaluation of the sample size as defined in [Section 10.5](#). Details of unblinded roles will be provided in a separate Unblinding Guidance Document. Upon observation of a safety event that requires knowledge of IP assignment to determine event causality and further action and/or treatment (e.g., SUSAR), the Sponsor's Medical Monitor may be unblinded to IP assignment. A procedure for emergency access to a subject's treatment assignment within the interactive voice response system will be provided. The unblinding of any blinded team member will be documented.

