1. INTRODUCTION AND OBJECTIVES OF ANALYSIS

1.1. Introduction

This document presents the statistical analysis plan (SAP) for Synlogic, Protocol SYNBI020-CP-002: A Randomized, Double-blind, Placebo-controlled Study to Assess the Safety, Tolerability, and Pharmacodynamics of SYNBI020 in Hepatic Insufficiency and Cirrhosis Patients.

This SAP is based on the final protocol (version 6) dated 27 November 2018.

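### The protocol and SAP give different Part 2 sizes, SDs and re-sizing rules for ammonia, and the SAP contradicts itself on the SD, alpha, interim boundary and sizes

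*Protocol*

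**What the plan says.** **Protocol.** Section 10.5 states: "A sample of 24 subjects must complete all 3 ammonia AUC intervals". The target is a 20% reduction from 70 µmol/L at about 10% significance and 90% power. It continues: "The number of subjects assumes that the standard deviation (SD) of spot ammonia is 36.4" µmol/L. Half the variance is taken as between subjects, and the SD of average daily ammonia as possibly half the spot SD. On adaptation, "up to 2 interim analyses for sample size re-estimation may occur after at least 12 subjects have completed all ammonia AUC assessments", and the Part 2 total "may be increased up to 40 at either point based on the SD of data observed". Section 5.1 repeats the range: "Approximately 24 to 40 evaluable subjects, defined as subjects who complete all 3 ammonia 24-hour AUC intervals". No efficacy boundary, futility boundary or conditional-power rule is given. Section 10.6 appoints an unblinded observer and says "this individual will be responsible for re-evaluation of the sample size as defined in" Section 10.5.

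**SAP.** Section 4.1 requires 16 completers for the same effect, significance and power, with the spot SD now 9. Section 4.3 plans:
- an unblinded interim at 16 and a final size (N_CP) of at least 20;
- a possible efficacy stop at p < 0.028 and a possible futility stop at conditional power below 30%;
- otherwise re-sizing to 90% conditional power, up to 40.

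On sample size, Section 5 records only a change in the number of subjects for the interim.

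**Version.** SAP 1.1 states: "This SAP is based on the final protocol (version 6) dated 27 November 2018". The version of the supplied protocol cannot be seen.

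**The concern.** Two documents that should describe one design give different required sizes, different SDs and different quantities that drive re-sizing. Protocol 10.6 sends the unblinded observer to the observed-SD rule, while SAP 4.3 prescribes conditional power. The same interim data could therefore lead to different enrolment decisions.

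The SAP also cannot be executed as a single plan, because its own sections disagree on the SD, the interim threshold, the total alpha, the re-sizing basis and the sizes. These rules govern an unblinded, data-driven decision, so any ambiguity left at the interim would be resolved by someone who has seen the data.

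**Working it through.** **1. Reproduce the protocol's 24.**
- Inputs (Protocol 10.5): effect 0.20 × 70 = 14; spot SD 36.4; halved for the daily average, 18.2; half the variance within subject, 18.2 × √0.5 = 12.87. The protocol does not print 18.2 or 12.87; they are derived.
- Assumption: one-sided 0.10, from SAP 4.2.1. The protocol gives no side.
- Per arm: n = 2(1.282 + 1.282)² × 12.87² / 14² = 11.1, so 12 per arm and 24 in total. The two-sided version gives 30.

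**2. Power at each size.** Fixed size, two equal arms, noncentral t with N − 2 df, noncentrality 14 / (SD × √(4/N)), one-sided 0.10:

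| SD used for the analysed outcome | N = 16 | N = 20 | N = 24 |
|---|---|---|---|
| 12.87 (reproduces 24) | 79.6% | 86.3% | 90.9% |
| 9 as the outcome SD | 95.9% | 98.3% | – |
| 9 as a within-subject residual: 9 × √1.5 = 11.0 | 88.1% | 93.2% | – |

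The factor √1.5 is for baseline subtracted from the mean of Days 5 and 6, with independent within-subject errors. With 9 as the outcome SD and two-sided 0.10, N = 16 gives 90.5%.

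**3. SAP 4.1 as printed.** A spot SD of 9, halved, with about half the variance between subjects, gives 9/2 × √0.5 = 3.2. Four subjects in total would then give 97.5% power. This text cannot be the source of 16.

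**4. The SAP against itself.**

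| Item | One place | Another place |
|---|---|---|
| What 9 is | Prior-study spot SD (4.1) | SD of the difference in means (4.3); Stage 1 within-subject residual (6.4: 0.1324 × 64.8 = 8.6) |
| Spot SD | 9 (4.1) | About 26 (6.4) |
| Interim efficacy p | 0.01 (4.2.5) | 0.028 (4.3, 6.4) |
| Total one-sided alpha | 0.10 (4.2.1, 4.2.5, 6.4) | 0.05 (4.3, for c2) |
| Re-sizing basis | Observed SD (2.1) | Conditional power (4.3) |
| Interim / final size | 12 / 16 (opening of 6.4) | 16 / 20 (4.3) |

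The 24/30 plan mentioned in SAP 4.3 is described there as replaced and is not counted.

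**5. Final critical value.** Interim and final Z are bivariate normal with correlation √0.80. Solving for the total rejection probability at t = 16/20 gives |c2|:

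| Spent at interim | Total 0.10 | Total 0.05 |
|---|---|---|
| 0.028 | 1.293 | 1.726 |
| 0.01 | 1.282 | 1.652 |

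The SAP prints 1.904 in absolute value. With 0.028 spent, that gives a total one-sided alpha of 0.040, which matches neither stated total.

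**6. The SAP 6.4 table.** At SD 9 it reports 99.12% efficacy stopping at N = 16. With n per arm, the normal approximation is Φ(14 / (9 × √(2/n)) − 1.911). For 8 per arm: Φ(3.111 − 1.911) = 88.5%. For 16 per arm: Φ(4.400 − 1.911) = 99.4%. The printed figure is close to the second.

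**The case against.** The strongest reply is that this is a Phase 1b/2a trial whose primary objective is safety, the protocol calls its alpha and power approximate, and it defers analysis detail to the SAP. An interim at 16 fits the protocol's wording (at least 12 completers), Protocol 10 allows further interims, and Protocol 8.1 lets the sponsor discontinue. The supplied protocol may also not be version 6: for screening it says "The screening period for all subjects will be up to 45 days prior to admission to the inpatient facility", while SAP 4.2.9 says 30 days. All of this stands. A version mismatch could explain part of the gap between the documents. It does not explain the SAP's disagreements with itself.

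Three stronger readings are tempting and not supported.
- **That the residual reading of 9 is the basis for 16.** It gives 88.1%, but 9 as the outcome SD at two-sided 0.10 gives 90.5%. SAP 4.2.1 says one-sided 0.10, yet the total one-sided 0.05 used for c2 in 4.3 corresponds to two-sided 0.10. The documents do not settle it.
- **That the two documents set conflicting stopping boundaries.** The protocol sets none for ammonia. The 0.01 against 0.028 conflict lies within the SAP, and the stops in SAP 4.3 are permissive.
- **That Part 2 is underpowered.** The 79.6% and 86.3% are fixed-size figures. The adaptive design can grow to 40.

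**Conclusion.** The concern holds. The supplied documents state required sizes of 24 and 16 and a planned final size of at least 20 for one comparison, on different SDs and different re-sizing rules. At the protocol's derived SD, moving from 24 to 16 costs about 11 percentage points of fixed-size power (90.9% to 79.6%), and moving to 20 costs about 5 (86.3%). The SAP's stated derivation of 16 is wrong as printed, and its c2 matches neither of its alpha totals.

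A reader might take the table's 99.87% overall power at SD 9 as reassurance. Its 99.12% efficacy stop does not reproduce with 16 subjects in total. The nearness to 16 per arm suggests, but does not prove, a mix-up of per-arm and total sizes. The table's powers should not be relied on until it is rerun.

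These results rest on one-sided 0.10, an effect of 14 and, for the residual reading, independent within-subject errors. How much of the gap between the documents is a version difference is unknown.

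**What to change.** 1. Confirm whether the supplied protocol is the version 6 that the SAP cites.
2. State one required size, one sourced SD, one total one-sided alpha, one interim boundary and one re-sizing basis. Use them in Protocol 10.5, 10.6, 4.1, 5.1 and the synopsis, and in SAP 2.1, 4.1, 4.2.5, 4.3 and 6.4.
3. In SAP 4.1 and 4.3 say what 9 is. If it is the Stage 1 residual, delete the prior-study source and the halving from 4.1.
4. If the SAP design is kept, replace 1.904 with the value from step 5 of the working for the chosen alpha and interim spend, and recompute it if N_CP changes.
5. Rerun the SAP 6.4 table with interim and final sizes confirmed as totals, and restate power under both 9 and the protocol's SD.
6. List the SD, size, stopping and re-sizing changes in SAP Section 5.

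The mortality stopping rule, printed in both documents, gives counts only for 24 and 40 subjects. That passage must be reconciled with the chosen size.

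The cost is document amendments and a simulation rerun. Stated power may look less favourable. No enrolment beyond the 40 already allowed is needed.

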10.6. Randomization and Blinding

Part 1: Open-label, all subjects will receive SYNB1020. Neither subjects nor investigators are blinded.

Part 2: Subjects will be randomized in a 1:1 ratio to receive either SYNB1020 or placebo. Randomization will be performed using a computer-generated central randomization scheme maintained by the Sponsor or designee. Both subjects and investigators will be blinded to study compound assignment, as will all other study personnel, with the exception of one unblinded pharmacist at the study site(s). In addition, an unblinded observer will be assigned to this study and will be independent of the study team. The unblinded observer will be able to review unblinded data as needed to aid in study progress, and this individual will be responsible for re-evaluation of the sample size as defined in [Section 10.5](#). Details of unblinded roles will be provided in a separate Unblinding Guidance Document. Upon observation of a safety event that requires knowledge of IP assignment to determine event causality and further action and/or treatment (e.g., SUSAR), the Sponsor's Medical Monitor may be unblinded to IP assignment. A procedure for emergency access to a subject's treatment assignment within the interactive voice response system will be provided. The unblinding of any blinded team member will be documented.

10.7. Changes in the Conduct of the Study or Planned Analysis

Only the Sponsor may modify the protocol. Amendments to the protocol will be made only after consultation and agreement between the Sponsor and the Investigator. The only exception is when the Investigator considers that a subject's safety is compromised without immediate action. In these circumstances, the Investigator should inform the Sponsor and the full IRB within 1 working day after the emergency occurred. All amendments that have an impact on subject risk or the study objectives or require revision of the informed consent document must receive approval from the IRB prior to implementation.

11. DATA RECORDING, RETENTION AND MONITORING

11.1. Case Report Forms

Data will be collected using source documents through an electronic data capture (EDC) system at the clinical site. The Investigator or designee will record data specified in the protocol using eCRFs. Changes or corrections to eCRFs will be made by the Investigator or an authorized member of the study staff according to the eCRF completion guidelines. It is expected that the site will enter all data within 5 days of a subject visit.

It is the Investigator's responsibility to ensure eCRFs are complete and accurate, regardless of whether this responsibility has been delegated in whole or in part. Following review and approval, the Investigator or designee will electronically sign and date the pages, which certifies that the Investigator has thoroughly reviewed and confirmed all data on the eCRF.

11.2. Data Retention

Data retention practices will follow International Council for Harmonisation of Technical Requirements for Pharmaceuticals for Human Use (ICH) guidelines, which note that essential documents should be retained for a minimum of 2 years after the last approval of a marketing application in an ICH region and until there are no pending or contemplated marketing applications in an ICH region or at least 2 years have elapsed since the formal discontinuation of clinical development of the IP. However, these documents should be retained for a longer period if required by the applicable legal requirements.

11.3. Data Monitoring

This study will be closely monitored by representatives of the Sponsor or designee throughout its duration. Monitoring will include personal visits with the Investigator and study staff as well as appropriate communications by telephone, fax, mail, email, or use of the EDC system, as applicable. It is the monitor's responsibility to inspect eCRFs at regular intervals throughout the study to verify the completeness, accuracy, and consistency of the data and to confirm adherence to the study protocol and to Good Clinical Practice (GCP) guidelines. The Investigator agrees to cooperate with the monitor to ensure that any problems detected during the course of this study are resolved promptly. The Investigator and site will permit study-related monitoring, audits, IRB review, and regulatory inspection, including direct access to source documents.

It is understood that study monitors and any other personnel authorized by the Sponsor may contact and visit the Investigator and will be permitted to inspect all study records (including eCRFs and other pertinent data) on request, provided that subject confidentiality is maintained and that the inspection is conducted in accordance with local regulations.

Every effort will be made to maintain the anonymity and confidentiality of subjects during this study. However, because of the experimental nature of the IP, the Investigator agrees to allow representatives of the Sponsor and authorized representatives of regulatory authorities to inspect the facilities used in the conduct of this study and to inspect, for purposes of verification, the hospital or clinic records of all subjects enrolled in the study.

